We propose a proof-of-concept (phase 2) double-blind randomized placebo-controlled trial to evaluate the efficacy and short-term safety of ramelteon for the prevention of postoperative delirium in a high-risk group of patients, 65 years and older, with MMSE²⁵ scores ≥ 15 , planned orthopedic surgery. Our prior work demonstrates the feasibility of conducting a prevention trial in this population, using state-of-the-art delirium detection and diagnosis methodology.^{5,25} Should this preliminary trial, show evidence of efficacy and adequate safety, then a phase 3 trial will be proposed.

Our group has demonstrated that an early predictor of subsequent delirium is the presence of delirium immediately upon recovery from general anesthesia in the post anesthesia care unit (PACU).^{5,26,27} The proposed trial will incorporate assessment of PACU delirium as a means of early delirium detection in helping to determine the efficacy of the ramelteon intervention.

2. **Objectives (include all primary and secondary objectives)** The proposed trial will involve administering 8 mg ramelteon orally (1 dose preoperatively and 2 doses postoperatively) or placebo in 80 older-aged patients to test the following:

Specific Aim 1 (primary outcome): To compare delirium incidence and severity between ramelteon and placebo using the DSM 5 criteria by expert panel consensus.

Hypothesis 1: Compared to placebo, ramelteon will be associated with a) a lower incidence and severity of postoperative delirium immediately upon recovery from anesthesia in the PACU, and b) with a lower incidence and severity of delirium on postoperative day (POD) 1 and POD 2.

Specific Aim 2 (safety outcome): To compare adverse events (AEs) and serious adverse events (SAEs) between ramelteon and placebo.

Hypothesis 2: Ramelteon will have an adequate safety profile in this postoperative cohort, sufficient to support conducting a larger prevention trial. Specifically, compared to placebo, ramelteon will not be associated with increased incidence of postoperative delirium or with increased adverse side effects including fatigue, headache and next day somnolence during the treatment episode.

3. Background (briefly describe pre-clinical and clinical data, current experience with procedures, drug or device, and any other relevant information to justify the research)

a. Significance:

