Outcome Measure Specific Aim I – State-of-the-Art Delirium Assessment and Diagnosis: Well-trained research staff will conduct delirium assessments at baseline, to exclude cases of prevalent delirium, and at three later time points (see Figure and Table). This assessment includes: (1) face to face standardized interview of the patient regarding experiences, (2) standardized cognitive testing including the MMSE⁷⁵ and the abbreviated Digit Span,⁸⁰ (3) history from family/friends familiar with the patient’s cognitive baseline, (4) interview of nursing and other medical staff caring for the patient, and (5) review of medical records for evidence of behavioral disturbances and symptoms in previous 24 hours. Information on sleep disturbance is sought from all sources and is a symptom of delirium. Assessors will rate the CAM⁸¹ and the Delirium Rating Scale-Revised ’98 (DRS-R98)⁶² for the prior 24 hours and describe the patient’s behavior and mental state in a written narrative. If a patient is intubated the CAM-ICU⁸² will be administered to determine delirium status. Patients who are comatose will be documented as such. (Preliminary data suggests that this is a rare occurrence <1%) Final adjudication of delirium diagnosis is derived after all data is presented to a panel of expert delirium diagnosticians ([name]).

The primary diagnosis of delirium is based upon meeting all DSM-5 criteria (see appendix), and is determined by consensus of the expert panel - a method currently employed by this group of co-investigators in the STRIDE study.

A second outcome measure will be analyzed using the continuous variable of delirium severity derived from the DRS-98R severity measure.

Outcome Measure Specific Aim II- Adverse Events: All adverse events (AE and SAE) will be collected from the medical record and daily patient assessment using a customized instrument (“Health Questionnaire”) which will systematically probe for known side effects (fatigue, headache and next day somnolence) (see Protection of Human Subjects). Assessment of Outcome and Covariates:

Table: Timing and Content of Patient Assessments

Assessments	Administration	Collection Instrument and Source
Cognition	Preoperative, PACU POD 1 and 2	Mini Mental State Exam Abbreviated Digit Span: Forwards and Backwards
Delirium	Preoperative, PACU, POD 1 and 2	CAM (full) ⁸³ after patient exam + proxy/medical record review or CAM-ICU if intubated; DRS-98R (severity measure)

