Analysis 2: The continuous DRS-98R severity measure of delirium will be modeled via longitudinal linear regression with correlated observations within participants addressed via the method of GEE with treatment assignment as the covariate of interest and controlling for baseline DRS-98R score, MMSE, surgical duration and sleep disorders.

Data Analysis-Specific Aim 2: Risk of a severe adverse event will be modeled as a function of treatment assignment using logistic regression, as will counts of total adverse events using ordinal logistic regression or Poisson regression as appropriate. Counts of each specific type of AE, as a function of treatment assignment will be scrutinized to determine the power needed to study them in future larger-scale trials.

- d. Early stopping rules. This is a pilot study and will continue until 80 adherent participants are recruited. A Data Safety Monitoring Board will review the data at the end of year one or at recruitment of 40 adherent participants (whichever comes first) to review the unblinded (labelled "A" and "B") data for safety of the intervention. Specifically, for the analyses of rates of delirium in the two groups, we will use a Haybittle-Peto boundary such that the alpha for the interim analysis will be 0.001, and the alpha for the final efficacy analysis will be 0.05.

8. Risks

- a. Medical risks, listing all procedures, their major and minor risks and expected frequency.

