Risks associated with the Study Treatment: Ramelteon has FDA approval for use in elderly patients with insomnia. However this agent has never been used peri-operatively in older patients undergoing general or regional anesthesia and we cannot be certain that it will be safe in this setting. Therefore the study aims to test safety of this agent compared to placebo; we will systematically collect daily information on adverse (AE) and serious adverse events (SAE) that occur in each arm of the study. The main potential risk is one of increased incidence of delirium due to the treatment intervention. Other risks associated with the use of ramelteon reported in product labeling include: 1) angioedema and anaphylactic reactions – this risk is extremely rare; 2) worsening of insomnia, or the emergence of new cognitive or behavioral abnormalities that may be the result of an unrecognized underlying psychiatric or physical disorder, such as worsening of depression (including suicidal ideation and completed suicides), hallucinations, bizarre behavior, agitation and mania; 4) amnesia, anxiety and other neuro-psychiatric symptoms may also occur unpredictably, including complex behaviors such as "sleep-driving" (i.e., driving while not fully awake after ingestion of a hypnotic) and other complex behaviors (e.g., preparing and eating food, making phone calls, or having sex) with amnesia for the event; 5) decreased testosterone levels and increased prolactin levels have been reported with long-term use; 7) the use is contraindicated in severe hepatic failure as evidenced by cirrhosis, ascites, portal hypertension and prolonged bleeding times; 8) also contraindicated with the concomitant use of fluvoxamine; and finally 9) caution is to be used when prescribing with other CYP enzyme active agents such as rifampin, fluconazole, and ketoconazole. Other less serious side effects that have been reported in clinical trials include somnolence, fatigue, dizziness, nausea and worsened insomnia.

The following is taken from the ramelteon package insert:

ADVERSE REACTIONS

The following serious adverse reactions are discussed in greater detail in other sections: Severe anaphylactic and anaphylactoid reactions [see Warnings and Precautions (5.1)] Abnormal thinking, behavior changes, and complex behaviors [see Warnings and Precautions (5.3)] CNS effects [see Warnings and Precautions (5.4)]

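### Aim 2 safety analysis names severe where the aim and data collection say serious, and Hypothesis 2 (no increase in harm) has no interval-based criterion, so a non-significant result at 40 per arm could be misread as adequate safety

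*Combined protocol and SAP*

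**What the plan says.** Section 2 gives Specific Aim 2 as: "To compare adverse events (AEs) and serious adverse events (SAEs) between ramelteon and placebo". Hypothesis 2 then states: "Ramelteon will have an adequate safety profile in this postoperative cohort, sufficient to support conducting a larger prevention trial". It spells this out by saying, relative to the control arm and over the treatment period, that "ramelteon will not be associated with increased incidence of postoperative delirium or with increased adverse side effects including fatigue, headache and next day somnolence".

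Section 7.a describes collection in the same terms as the aim: "All adverse events (AE and SAE) will be collected from the medical record" and from daily patient assessment. The assessment table lists forms for SAEs and AEs. Section 8.a also speaks of serious adverse events and adds: "Therefore the study aims to test safety of this agent compared to placebo".

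The analysis is in section 7.c, Data Analysis-Specific Aim 2: "Risk of a severe adverse event will be modeled as a function of treatment assignment using logistic regression". Total adverse event counts get ordinal logistic or Poisson regression. Counts of each specific event type are to be examined by arm, with the stated purpose of working out the power that later, larger trials would need. Delirium is modelled under Aim 1, again as a treatment effect. Section 7.c gives no alpha, margin, confidence-interval criterion or power for Aim 2, and no definition of adequate safety. Every power figure in the section concerns efficacy.

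**The concern.** There are two linked problems.

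First, the variable to be modelled is not the one in the aim. Seriousness and severity are different classifications: an event can be severe without being serious, and the reverse. Since the plan describes no severity grading, a severe-event variable cannot be derived from the data as described. Read literally, serious events have no planned comparison of their own.

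Second, Hypothesis 2 is a claim of no increase, and it is meant to be "sufficient to support conducting a larger prevention trial". A model of the treatment effect can show harm, but failing to show harm does not establish its absence. That would take a statement of how large an excess the data rule out, and the plan has none. At stake is one of the two conditions that section 1 sets for proposing phase 3. A null safety comparison in a small trial might be cited as reassurance that it cannot give.

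**Working it through.** **Terminology.** Objectives (section 2): adverse and serious adverse events. Collection (7.a and its table): AE and SAE. Risks (8.a): serious adverse events. Analysis (7.c): severe adverse event. Only the analysis sentence differs.

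**Inputs.** 40 per arm, and delirium at 30% on placebo (7.c). Package-insert rates (8.a, Table 1): 2% placebo against 3% ramelteon for somnolence, fatigue, nausea and worsened insomnia; 3% against 4% for dizziness. Section 7.c states alpha 0.05 for efficacy only; I assume two-sided 0.05 here. The 5%, 6%, 10% and 20% event rates and the 45% and 60% delirium rates are my assumptions.

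**Method.** For each pair of true rates, sum the binomial probabilities of all pairs of counts (i, j) out of 40 for which |i − j|/40 ÷ √(2p̄(1 − p̄)/40) ≥ 1.96, with p̄ = (i + j)/80. This is the exact power of the uncorrected Pearson test.

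**Plan's own figures first.** 30% vs 6% gives 0.845, against the stated 0.84. 30% vs 3% gives 0.956, against the stated value above 0.90. The method reproduces the plan, so it is a fair yardstick for safety.

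**Power for harm at 40 per arm.**

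| Placebo vs ramelteon | Source of rates | Power |
|---|---|---|
| 2% vs 3% | section 8.a | 0.017 |
| 3% vs 4% | section 8.a | 0.030 |
| 3% vs 6% | assumed doubling | 0.079 |
| 5% vs 10% | assumed doubling | 0.146 |
| 10% vs 20% | assumed doubling | 0.247 |
| Delirium 30% vs 45% | 30% from 7.c, 45% assumed | 0.28 |
| Delirium 30% vs 60% | 30% from 7.c, 60% assumed | 0.80 |

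For the three assumed doublings of a single uncommon event, the chance of a non-significant result is therefore 75% to 92%. Fisher's exact test is lower still (for example 0.043 for 5% vs 10%).

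**What equal observed rates would exclude.** With 4/40 in each arm, the two-sided 95% Wald upper limit for the excess is 1.96 × √(2 × 0.1 × 0.9/40) = 0.131, about 13 points. The Newcombe interval gives 14.4 points. With 12/40 in each arm (30%, as for delirium), Newcombe gives 19.5 points. With 0/40 in each arm it gives 8.8 points.

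**Larger analysis set.** Intention-to-treat includes all randomised participants, so it may exceed 80. At an assumed 50 per arm, every power in the table apart from the 30% vs 60% row is at most 0.34.

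**The case against.** The strongest reply is that this is a self-described pilot, and that the plan nowhere says a non-significant result means safe. That is correct. Section 7.c says risk will be modelled and attaches no p-value rule to Aim 2; a logistic or Poisson model yields an interval as readily as a p-value. A reader might infer that non-significance *will* be taken as adequate safety. The documents do not support that; they only leave the reading open by giving no other criterion. Section 1 also makes phase 3 depend on evidence of efficacy as well, so a safety result alone would not trigger it.

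A reader might also infer that the trial would miss real harm in general. That is too strong. Delirium, which section 8.a treats as the main risk, would be detected with power of about 0.80 if it doubled from 30% to 60%. Total event counts may also be more informative. With assumed Poisson counts averaging 1 per placebo patient, a doubling gives a log rate ratio of 0.693 with standard error √(1/40 + 1/80) = 0.194, and power of about 0.95. With variance twice the mean, this falls to about 0.72.

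The sentence on specific event types shows that the authors know power is low for fatigue, headache and somnolence, and no test of them is planned. But Hypothesis 2 names exactly these effects, and counting them for future planning sets no standard by which that hypothesis could be judged. The data safety monitoring board's interim review does not supply one for the final analysis either.

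Finally, *severe* is very likely a slip, and it would be wrong to conclude that the authors chose a different endpoint. It still has to be corrected, because no other sentence defines the analysis.

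**Conclusion.** Wrong as written (minor). The analysis sentence names a class of event that the plan does not describe grading, and it must be reconciled with the serious adverse events of the aim and the collection forms. Separately, the planned analyses cannot establish the no-increase statement in Hypothesis 2, because no interval or other criterion links the results to that statement.

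The limitation applies to uncommon single events (power 0.02 to 0.03 at the documents' own rates, 0.08 to 0.25 for an assumed doubling from 3%, 5% or 10%) and to moderate rises in delirium (0.28 for 30% to 45%). It does not apply to very large harms. Identical observed rates of 10% would still be compatible with an excess of about 13 to 14 points. These figures rest on 40 per arm, a two-sided 0.05 level and the labelled assumed rates; a modestly larger intention-to-treat set does not change the conclusion.

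**What to change.** In section 7.c, under Data Analysis-Specific Aim 2:

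- Replace *severe* with *serious*. If severity is also wanted, define and grade it separately.
- For serious adverse events, fatigue, headache, somnolence and delirium, report the risk difference (ramelteon minus placebo) with its two-sided 95% confidence interval. Newcombe's method suits small counts.
- Word the Hypothesis 2 conclusion as the largest excess that the upper limit excludes for each event, or state that Aim 2 is descriptive.
- State that p > 0.05 will not be interpreted as adequate safety.

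This needs no extra participants or data: a few sentences of SAP text and one small table. The downside is a more modest safety claim at the end of the trial.

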Choice of study population and outcome measurement time points: Delirium, diagnosed early in recovery from anesthesia, is very common in older adults (45% after recovery from general anesthesia) and predicts delirium in the subsequent postoperative course.^{5,26,27,73} This finding runs contrary to the view that postoperative delirium cannot be diagnosed unless a period of lucidity has occurred following recovery from anesthesia, and that commonly observed confusion and uncooperativeness upon recovery are benign emergence phenomena.⁷⁴ Since **our previous work suggests that the syndrome, regardless of its attribution, predicts delirium in the days following surgery as well as measurable changes in cognitive function,**⁵ we have included two time periods of delirium incidence as our primary outcome: 1) in the PACU after recovery of arousal, hemodynamic, and respiratory function after anesthesia, as measured by Aldrete score \geq 8;⁷⁴ and 2) during POD 1 and 2 independent of status in the PACU. This will allow for the study of preoperative ramelteon on immediate recovery and during the traditionally described delirium incidence in the days following surgery. For participants who discharge early from the hospital (prior to POD 2), delirium assessment will be conducted via telephone. While longer-term follow-up beyond POD 2 is desirable, it is difficult to complete in all patients in this preliminary study due to an institutional trend toward early post-surgery discharge. We plan to recruit patients with significant cognitive impairment at baseline (mild to moderate dementia) by including participants with Mini Mental State Exam (MMSE) scores \geq 15.⁷⁵ Based upon our previous work, distribution of MMSE scores of 24-30, 15-23, and < 15 prior to surgery for this population will be 50-60%, 25-33% and 7-25% respectively. Participants who score below this cut-off are increasingly difficult to test, making delirium diagnosis difficult.

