Randomization: A statistician ([name]) will be responsible for design, implementation, and maintenance of randomization procedures that assign participants to active pharmaceutical or placebo. Since preoperative cognitive impairment is consistently and strongly associated with the development of postoperative delirium, our randomization process will stratify by preoperative MMSE exam score to ensure balanced allocation (MMSE score 24/30 - 30/30 and 15/30 - 23/30). Under supervision of the statistician, research pharmacy staff who have no contact with the patient or clinical staff will randomize participants using a computer program, utilizing dynamic allocation probabilities to balance the two groups on the dichotomous MMSE variable.

Masking Procedures: The research pharmacy staff will prepare the active treatment (ramelteon 8 mg) and placebo using identical gel caps containing 100 mg riboflavin for doses to be self-administered outside of the hospital. No riboflavin will be added to study doses to be administered by hospital nursing staff. Once randomized, the assigned agent will be labeled with the patient's name and medical record number with the administration instructions consistent with hospital policy. No markings will indicate identity of the agent. Participants admitted on the day of surgery will receive the assigned study medication (active treatment/placebo) at the study visit prior to surgery. For all inpatient doses clinical nursing staff will administer medication each evening (8-10 pm). Administration will be documented in the clinical electronic medication record and adherence closely monitored by research staff.

Concomitant Medications: All medications except those enumerated in exclusions will be allowed.⁶⁰

Choice of Clinical Site and Feasibility of Recruitment: A total of 198 infection-free inpatients ≥ 65 years of age, underwent total hip or knee arthroplasty or revision under general anesthesia between 01/01/14-12/31/14 at JHBMC. The median (IQR) ASA physical status score and median surgical duration (IQR) was 3 (3-3) and 172 (122-216) mins. respectively, reflecting significant comorbidity and lengthy surgical times, consistent with high postoperative delirium risk likely to be at least 30%.⁵⁸

b. Study duration and number of study visits required of research participants.

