Choice of Sample Size; Power Considerations– Why 80 adherent participants? The power to detect a difference in the development of postoperative delirium of an the previously reported effect-size²⁴(30% placebo-treated vs. 3% ramelteon-treated) is greater than 0.90, using the current design of 40 participants in each treatment arm and assuming 30% of the placebo-treated group will develop delirium on POD 1 or 2. This design can detect an 80% reduction in delirium (30% placebo-treated vs. 6% ramelteon-treated) with a power of 0.84. A conservative estimate for power for the continuous outcome (DSRS-98R) measuring delirium severity can be derived by conceptualizing the proposed longitudinal analysis as an independent samples t-test. With alpha of 0.05 and a sample size of 80, and with means in the ramelteon and placebo groups of 5.75 and 11.34, respectively (as reported in Hatta, et al), and SDs of 4.16 and 10.96, we would have 84% power to detect that difference. Power for the planned analysis, which includes 3 post-surgery measurements per participant, and controls for baseline measurement and additional covariates would likely be greater.

Data Analysis-Specific Aim 1:

Analysis 1: Odds of postoperative delirium upon immediate recovery will be modeled via logistic regression with treatment assignment as the covariate of interest, and controlling for baseline MMSE, surgical duration and sleep disorders in all randomized participants in a strict intent to treat model and also in a second analysis among the 80 first-dose adherent participants.⁹¹ Odds of delirium on POD's 1 and 2 will be modeled via a Markov logistic regression model⁹² as a function of treatment assignment, baseline MMSE, and mental status on

the previous day, where two transitions are possible: from normal mental status to delirium and/or coma (abnormal mental states) and the reverse. Correlation of mental status on consecutive days for the same individual will be modeled using generalized estimating equations (GEE).⁹² We will fit models with interactions between treatment group and variables hypothesized to predict treatment response, including baseline MMSE and sleep to determine if treatment response varies as a function of baseline predictors.

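### Aim 2 safety models omit the MMSE stratum used to balance allocation; if MMSE predicts adverse events, the logistic and ordinal tests would be somewhat conservative for harm

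*Combined protocol and SAP*

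**What the plan says.** Under Study Procedures (4.a, Randomization), the protocol states that "our randomization process will stratify by preoperative MMSE exam score to ensure balanced allocation", with strata MMSE 24-30 and 15-23. A computer program does this, "utilizing dynamic allocation probabilities to balance the two groups on the dichotomous MMSE variable". The reason given is that "preoperative cognitive impairment is consistently and strongly associated with the development of postoperative delirium".

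Section 7.c carries that factor into all three Aim 1 models. The PACU delirium model is fitted "controlling for baseline MMSE, surgical duration and sleep disorders in all randomized participants", the Markov model for POD 1 and 2 includes baseline MMSE, and so does the longitudinal model for delirium severity.

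The Aim 2 paragraph of 7.c differs. It states "Risk of a severe adverse event will be modeled as a function of treatment assignment using logistic regression", and continues "as will counts of total adverse events using ordinal logistic regression or Poisson regression as appropriate". No covariate is named for either model, nothing elsewhere adds one, and no reason is given for departing from Aim 1. Section 7 states no expected event rate, alpha or power for Aim 2.

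**The concern.** Forcing the arms to be alike on a factor removes that factor's contribution to the chance difference between arms. If the factor also predicts the outcome, an analysis that omits it still counts the between-stratum variation as noise. The standard error is then too large for the design, and the test rejects less often than its nominal level.

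In an efficacy comparison that is a modest inefficiency. In a safety comparison it works in the unhelpful direction, because a true excess of events on ramelteon becomes harder to see. Hypothesis 2 asks whether the safety profile is good enough to support a larger trial, so Aim 2 is one of the two legs (with efficacy) on which that decision rests. The covariate is already collected and already used for allocation.

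**Working it through.** **Plan's own figure.** There is none for Aim 2. The nearest is the Aim 1 power of 0.84 for 30% versus 6% with 40 per arm. It reproduces at 0.844 (arcsine) and 0.837 (unpooled variance), with 0.810 for pooled variance. This confirms the 40-per-arm, two-sided 5% setting used below, but says nothing about Aim 2.

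**Inputs from the documents.** 40 per arm. Section 4.a (choice of study population) gives "distribution of MMSE scores of 24-30, 15-23, and < 15 prior to surgery for this population will be 50-60%, 25-33% and 7-25% respectively". After dropping scores below 15, the lower stratum is 25/(25+60) = 29% to 33/(33+50) = 40% of participants, or about 12 to 16 of 40 per arm.

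**Assumed inputs.** All adverse-event rates by stratum, the treatment effects, a two-sided 5% test, and exact or near-exact balance within stratum.

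**Step 1: direction, by arithmetic.** Let w be the lower-stratum share, and p_L and p_H the event risks in the lower and upper strata, with no treatment effect. The unadjusted test uses the total variance T = p(1 - p), where p = w·p_L + (1 - w)·p_H. With balance in each stratum, the real variance is the within-stratum part, W = w·p_L(1 - p_L) + (1 - w)·p_H(1 - p_H). The true rejection rate is about 2[1 - Φ(1.96/√(W/T))].

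- w = 0.30, risks 30%/10% (odds ratio 3.9): p = 0.16, T = 0.1344, W = 0.126, W/T = 0.9375. The critical value is effectively 2.02 and the size about 0.043.
- w = 0.35, upper risk 15%, odds ratio 6 (lower risk 51.4%): p = 0.2775, T = 0.2005, W = 0.1703, W/T = 0.849. The effective critical value is 2.13 and the size about 0.033.
- Equal risks: W = T, so the stratum causes no conservatism.

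**Step 2: size and power by simulation (unadjusted → stratum-adjusted).** Serious events at a treatment odds ratio of 3, with 12 lower-stratum participants per arm except where noted:

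| Lower/upper risk | Type I error | Power |
|---|---|---|
| 5%/5% (no link) | 0.042 → 0.039 | 0.289 → 0.262 |
| 20%/10% | 0.053 → 0.050 | 0.476 → 0.483 |
| 30%/10% | 0.045 → 0.049 | 0.479 → 0.509 |
| 30%/10%, 16 per arm | 0.045 → 0.049 | 0.492 → 0.531 |
| 50%/20% | 0.040 → 0.051 | 0.589 → 0.611 |
| 51%/15% (odds ratio 6, share 0.35) | 0.032 → 0.047 | 0.505 → 0.581 |

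The odds-ratio-6 row uses logistic likelihood-ratio tests; the others use score tests (Pearson versus Mantel-Haenszel). The simulated sizes agree with Step 1.

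Event counts by a rank score test standing in for ordinal logistic regression, with a 1.5-fold treatment excess, an upper-stratum mean of 1, no overdispersion, and 12-16 lower-stratum participants per arm:

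| Lower/upper count ratio | Type I error | Power |
|---|---|---|
| 1 | about 0.05 both ways | 0.48 both ways |
| 1.5 | 0.043-0.045 → 0.047-0.049 | 0.51-0.53 → 0.54-0.55 |
| 2 | 0.035 → 0.048-0.051 | 0.50-0.52 → 0.57-0.60 |

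Stronger assumed links cost more: at a count ratio of 3 the power loss is about 19-23 points. Nothing in the documents suggests a link of that strength.

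**Step 3: Poisson.** The model-based variance of the difference in totals is the sum of the two totals. Without overdispersion this already equals the sum of the within-stratum variances, so omitting the stratum does not inflate it. Simulated size stays near 0.05 at every count ratio.

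**Step 4: sparse events.** At risks of 15%/5%, the Wald logistic test rejects 0.005 of the time unadjusted and 0.008 adjusted under no effect. That conservatism comes from the small number of events, and the covariate barely changes it.

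**The case against.** The strongest reply is that the plan links MMSE to delirium and to nothing else. The delirium comparison, which the Risks section treats as the chief hazard of the intervention, is already MMSE-adjusted under Aim 1. What remains is mostly other events, whose relation to MMSE is undocumented. This stands, and it is why the point must be conditional. A reader might infer that the safety tests simply are conservative. The documents do not support that: with no link there is no loss, and at 5%/5% adjustment lowers power slightly. One qualification is that the plan does not say whether delirium and related events are left out of the Aim 2 counts. If they are counted, the plan's own statement makes the stratum prognostic for part of the outcome.

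A second reply is that an unadjusted comparison in a randomised trial does not inflate false positives, so this is a question of efficiency and not an error. That also stands. A reader might go further and suspect that allocation is predictable or the unadjusted analysis invalid. Neither follows: assignment is by computer through pharmacy staff with no patient contact, the trial is masked, and the unadjusted test errs only towards caution.

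Third, the Poisson option is unaffected. True; its own weakness runs the other way. With assumed gamma dispersion of 0.5-1, the model-based test had a type I error of about 0.11-0.28. That is a separate matter, which the stratum covariate is not meant to solve.

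Finally, dynamic allocation may balance less tightly than was simulated, which would shrink the effect.

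**Conclusion.** The point holds in conditional form and is a minor improvement. The design balances on MMSE, Aim 1 adjusts for it, and Aim 2 does not, without explanation. To the extent that MMSE predicts adverse events, the unadjusted logistic and ordinal comparisons would be conservative for detecting harm. The cost is about 1-4 power points at modest association, and about 6-8 points at a stratum count ratio of 2 or a serious-event odds ratio of about 6. It is zero if MMSE is unrelated to these events.

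The direction follows from the design. The size rests wholly on assumed event rates and treatment effects, because the documents give none for this population.

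**What to change.** In 7.c, Data Analysis-Specific Aim 2, add the randomisation stratum (MMSE 24-30 versus 15-23) as a covariate beside treatment in the event-count model and, where there are enough events to support two terms, in the event-risk logistic model. State in advance that when events are few the comparison will be a stratified exact one over the same two strata, or will stay unadjusted, since adjustment then gains nothing and may cost a little power. If the sponsor prefers to leave the stratum out, one sentence giving the reason would do.

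In the same edit, reconcile the event term: 7.c says severe, whereas Specific Aim 2 says serious.

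The cost is a sentence or two of text and one degree of freedom, with no new data or participants. The odds ratio becomes conditional on stratum and is no longer marginal, as is already the case in Aim 1.
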